4.2. Study design

- Main study: randomized controlled trial (RCT) on rESWT + RP vs. sham-rESWT + RP, with blinding of patients and evaluators/assessors, but without blinding of therapists applying the treatments (the rationale for this is provided in Section 4.11. *“Blinding of therapists and assessors”* below).

4.3. Inclusion criteria

- Adults (both male and female) with clinical and ultrasonographic diagnosis of acute HMC injury Type 3b.
- Age range: between 18 and 35 years.
- Physical conditions for rehabilitation (i.e., no surgery required)
- Willingness of the patient to participate in the study, and written informed consent signed and personally dated by the patient.
- No contraindications for rESWT.

4.4. Exclusion criteria

- Children and teenagers below the age of 18.
- Adults aged >35 years old.
- Patients with clinical and ultrasonographic diagnosis of acute HMC injury Type 3b who got injured more than seven days before potential enrollment into this study.
- Patients with clinical and ultrasonographic diagnosis of acute HMC injury Type 3A or Type 4.
- Bilateral acute HMC injury (Types 3A, 3B or 4).
- Proven or suspected HMC injury (Types 3A, 3B or 4) of the same lower limb in the time period of six months before potential enrollment into this study.
- Muscle injury caused by external impact on the back of the affected thigh (Category B according to Müller-Wohlfahrt et al., 2013).
- Surgery on the affected lower limb in the time period of one year before potential enrollment into this study.
- Acute or chronic lumbar pathology (because some cases of thigh pain may relate to spinal pathology; c.f. Linklater et al., 2010).
- No willingness of the patient to participate in this study, and/or written informed consent not signed and not personally dated by the patient.
- Contraindications of rESWT:
 - treatment of pregnant patients,
 - treatment of patients with blood-clotting disorders (including local thrombosis),

- treatment of patients treated with oral anticoagulants,
- treatment of patients with local bacterial and/or viral infections/inflammations,
- treatment of patients with local tumors, and
- treatment of patients treated with local corticosteroid applications in the time period of six weeks before the first rESWT session (if applicable).

4.5. Groups and treatments

All subjects will perform a specific rehabilitation program (RP) that will last for eight weeks, independent of the individual time interval to return to play (in line with Bayer et al., 2017). This RP was developed based on recommendations in the literature (Mendiguchia and Brughelli, 2011; Askling et al., 2014; Mendiguchia et al., 2017). The key objective of this RP is that after injury, the subject will develop functional, neuromuscular and biomechanical skills according to the demands of the sport she/he performs, while minimizing the risk of re-injury. Therefore, the proposed RP will take the subject through a combination of low-risk and high-demand movements, based on a systematic process. This process will consist of an orderly sequence of steps or phases – acute phase, subacute/regeneration phase, and functional phase). Each phase will depend on the outcome of the previous phase and will use the individualized response as criterion of progression. The RP will be controlled by the same physiotherapist who will not participate in the inclusion/exclusion process or any subsequent evaluation of the subject.

Acute phase

The goals of the acute phase include:

- prevent re-rupture at the injured site,
- prevent excessive inflammation and formation of scar tissue,
- increase tensile strength, adhesion and elasticity of new granulation tissue,
- reduce build-up of interstitial fluid, and
- detect and treat any lumbo-pelvic dysfunction.

Once a subject will be included in the proposed study she/he will be instructed to avoid the use of medication and apply the RICE principle (rest, ice, compression and elevation) three times per day in order to stop the injury-induced bleeding into the muscle tissue and thereby minimize the extent of the injury (see, e.g., Jarvinen et al., 2007).

With regard to the optimum time interval for starting active rehabilitation after acute HMC injury Type 3b Jarvinen et al. (2007) recommended immobilization for three to five days, followed by active mobilization. Bayer et al. (2017) pointed out that starting rehabilitation two days after injury rather than waiting for nine days shortened the interval from injury to pain-

free recovery and the time to return to play by approximately three weeks without any significant increase in the risk of reinjury. However, it is not known whether starting rehabilitation already two days after injury has any benefit over starting rehabilitation five days after injury. We will therefore follow the recommendation by Jarvinen et al. (2017) and progress to the sub-acute phase after five days.

The criterion for progression to the subacute/regeneration phase will be

- absence of pain five days after injury.

If the symptoms caused by the injured muscle persist for more than five days we will reconsider the existence of more extensive tissue damage and/or intramuscular hematoma that might require special attention and treatment by an orthopedic surgeon.

Subacute/Regeneration Phase

The goals of the subacute/regeneration phase include:

- improve overall core stability,
- improve strength and symmetry,
- reduce pain during prone isometric, isolated hamstring contractions at 15° knee flexion,
- improve hamstring flexibility of both legs,
- improve hip flexor flexibility of both legs, and
- improve neuromuscular control.

During the subacute/regeneration phase the subject will work on both legs daily during a single session. Exercises will be conducted to correct the different risk factors and mechanisms related to the lesion of the hamstring musculature. The exercises will be divided into four groups:

- core stability and lumbopelvic control,
- flexibility and neural mobilization,
- hamstring and gluteal strength, and
- running technique

(see also

http://wolterskluwer.http.internapcdn.net/wolterskluwer_vitalstream_com/MP4s/permalink/ms/a/mss_2017_02_28_mendiguchia_msse-d-16-00910r4_sdc1.mp4).

In addition, basic aerobic conditioning will start when the subject will be able to perform at least three sessions of the running technique without any discomfort or pain. Three running sessions per week will be performed at the clinic of the Principal Investigator and will include four sets of five minutes at a low to moderate intensity (individually rated by the subject). Suspension of running sessions will be permitted in the event of discomfort or pain.

The criteria for progression to the functional phase will be:

- no pain in prone position with knee flexed to 15°,
- no pain during slump test,
- < 10% asymmetry when in prone position with knee flexed to 15°,
- < 10% asymmetry during active knee extension test, and
- < 5° asymmetry in the modified Thomas Test.

Functional phase

The goals of the functional phase include:

- increase the optimum length of the hamstrings,
- decrease leg asymmetries in optimum length,
- decrease leg asymmetries in concentric hip extension,
- decrease leg asymmetries in horizontal force production during running, and
- improve torsional capabilities.

The functional phase will comprise daily exercises, with three sessions per week at the clinic of the Principal Investigator (every other day) and the remaining sessions at the club or at home. The exercises will comprise the following:

- core stability and lumbopelvic control,
- flexibility and neural mobilization,
- hamstring and gluteal strength,
- plyometric training, and
- running technique.

During the Functional Phase, the running session will consist of two sets of ten minutes at moderate to high intensity (individually rated by the subject). Suspension of running sessions will be permitted in the event of discomfort or pain.

The criteria for return to play will be (according to van der Horst et al., 2016):

- absence of pain on palpation,
- absence of pain during flexibility testing (active knee extension test and passive straight leg raise test),
- absence of pain during strength testing (isometric force test),
- absence of pain during and after functional testing (repeated sprint ability test and single leg bridge),
- similar hamstring flexibility,
- psychological readiness / athlete confidence, and
- clearance by the medical staff.

The quantity and quality of the supervised rehabilitation sessions at home or the sports club will be documented.

Patients in the rESWT group will receive the below:

- Specific rehabilitation program as outlined above.
- In addition: rESWT as follows:
 - nine rESWT sessions;
 - three sessions per week (interval between sessions: two or three days);
 - rESWT device: Swiss DolorClast (Electro Medical Systems, Nyon Switzerland), EvoBlue handpiece, 15 mm applicator;
 - 2500 rESWs per session, with energy density between 0.12 and 0.16 mJ/mm² (achieved by operating the Swiss DolorClast at air pressure between three and four bar), depending on what the patient tolerates;
 - rESWs applied at 15 Hz (i.e., 15 rESWs per second), resulting in treatment time between three and five minutes per session;
 - application of rESWs in prone position, with the patient lying on an examination table;
 - exact location of the application of rESWs determined by clinical and ultrasonographic examinations;
 - treatment of both the side of injury and the entire affected muscle (from distal to proximal in order to relax the affected muscle);
 - application of rESWs in sagittal (dorsal → ventral) direction; and
 - no use of local anesthesia.

Patients in the sham-rESWT group will receive the below:

- Specific rehabilitation program as outlined above.
- In addition: sham-rESWT as outlined above, with a specially designed placebo EvoBlue handpiece that looks and sounds like the EvoBlue handpiece of the Swiss DolorClast, but does not generate radial shock waves. This is achieved by blocking the projectile [“13” in Fig. 2] shortly before it strikes the metal applicator [“15” in Fig. 2]). The placebo EvoBlue handpiece will not emit any radial shock wave energy.

4.6. Recruitment of patients

- Patients in the rESWT group and the sham-rESWT group will be recruited from the Club Deportivo UAI Urquiza (Villa Lynch, Province Buenos Aires, Argentina) and will be recruited over the same period of time (approximately 12 months).
- Recruitment of patients will start immediately after approval of the study by the Ethics Committee of the Universidad Abierta Interamericana (Buenos Aires, Argentina).

- Officials of the Club Deportivo UAI Urquiza will be instructed that athletes who experience sudden, sharp pain in the posterior aspect of the thigh during training or competition shall immediately stop activity. These athletes will then be evaluated regarding the presence of the inclusion criteria of this study on the day of injury.
- All potential patients that fulfill the inclusion criteria and do not fulfill any of the exclusion criteria outlined above will be offered to participate in this study until the total number of patients (rESWT group: n=20; sham-rESWT group: n=20) will be recruited. Accordingly, the patients that will be prepared to participate in this study will be representative of the entire population from which they were recruited. We will report the proportion of those asked who agreed.
- The intervention will be undertaken in a specialist centre that is representative of the clinics most of the source population would attend if seeking treatment of acute HMCinjury Type 3b.

4.7. Informed Consent Process

Should patients agree to be part of this study, they will be guided through the informed consent process first, as described here. The Informed Consent Process will be done at the clinic of the Principal Investigator of this study ([name], [name]). A copy of the Participant Information Sheet will be given to them. The patient will be given sufficient time to read and understand everything written on the document. The Principal Investigator will be there to explain and answer any queries that may arise. The patient will sign the Informed Consent Form if agreeable thereafter.

4.8. Randomization and blinding of patients

- Patients that fulfill the inclusion criteria and do not fulfill any of the exclusion criteria will be randomly allocated to either rESWT + RP (n=20) or sham-rESWT + RP (n=20).
- Randomization will be performed as described by Rompe et al. (2008) in a randomized, controlled study on rESWT for Achilles tendinopathy. Specifically, a computerized random-number generator will be used to formulate an allocation schedule. Patients will be randomized to either treatment (rESWT + RP or sham-rESWT + RP), with use of the method of randomly permuted blocks. The randomization scheme will be generated with the use of the website, www.randomization.com. Fifty patients will be randomized into five blocks. A medical assistant at the clinic of the Principal Investigator will allocate interventions by means of opaque sealed envelopes that will be marked according to the allocation schedule. The medical assistant will be unaware of the size of the blocks.

- The randomized intervention assignment as outlined above will be concealed from both patients and health care staff until recruitment will be complete and irrevocable.
- Patients will be blinded in this study.
- The assessor will be blinded in this study. The assessor is the person who will assess the outcome of treatment during follow up. In this study, the assessor will be a medical assistant at the clinic of the Principal Investigator.
- The therapist will not be blinded in this study. The therapist is the person who will administer either rESWT or sham-rESWT to the patient. In this study, the therapist will be the Principal Investigator ([name]).

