4.10.2. Secondary clinical outcomes

Secondary clinical outcomes will be:

- individual patient's satisfaction at six months after inclusion into the study (using a scale ranging from 0 [maximum dissatisfaction] to 10 [maximum satisfaction]), and
- presence or absence of re-injury during a time period of six months after inclusion into the study (defined as sudden, sharp pain in the posterior aspect of the thigh that was initially injured, accompanied by the same objective criteria initially used for the diagnosis of acute HMC injury Type 3b).

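### Sections 4.8 and 4.9 do not keep allocation and treatment delivery apart from outcome assessment, so the text permits an assessor who knows the arm

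*Protocol*

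**What the plan says.** **Allocation (4.8).** "A medical assistant at the clinic of the Principal Investigator will allocate interventions by means of opaque sealed envelopes". The only information withheld from this person is the block size: "The medical assistant will be unaware of the size of the blocks".

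**Assessment (4.8).** "The assessor will be blinded in this study", and "the assessor will be a medical assistant at the clinic of the Principal Investigator". The same section makes the Principal Investigator the therapist, who is not blinded.

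**Patients (4.8).** "Patients will be blinded in this study". A separate bullet says that the assignment "will be concealed from both patients and health care staff until recruitment will be complete and irrevocable".

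**Visit procedures (4.9).** The Principal Investigator performs the randomization at the first visit. At all visits the Principal Investigator delivers the study treatment and also makes the efficacy assessment.

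**Blinding elsewhere.** Section 4.2 describes patients and assessors as blinded and therapists as not blinded. Section 4.11 says that every baseline and follow-up assessment is made by assessors who do not know the intervention.

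**Primary outcome (4.10.1).** Days to return to play. Return is allowed once several criteria are met: no pain on palpation or on flexibility, strength and functional testing; comparable hamstring flexibility; the athlete's confidence; and clearance by medical staff.

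**The concern.** The therapist cannot be blinded in this design, so a blinded assessor is the main protection against biased outcome assessment. That protection depends on who the assessor is, and the protocol never names a person who is clearly both the assessor and unaware of allocation. One route gives allocation and assessment to people with the same job title at the same clinic. The other gives the efficacy assessment to the person who delivers the treatment.

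The primary outcome is open to this kind of bias. It is a date, and the date depends on when someone judges the athlete to be pain-free, sufficiently flexible and fit to be cleared. An assessor who knows the arm can move that date without intending to. With 20 patients per arm compared by a Mann-Whitney test, the result would still be reported as coming from a blinded assessment.

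**Working it through.** The plan gives no figure on this point, so the check is a comparison of its own statements. The power calculation in 5.1 takes no account of who assesses, and the fix does not change it.

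**1. Who can know the arm?**

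| Role | Person named | Knows the arm? |
|---|---|---|
| Allocates from envelopes (4.8) | A medical assistant at the clinic | Not prevented; only block size is withheld |
| Performs randomization (4.9) | Principal Investigator | Yes, as therapist |
| Delivers active or sham treatment (4.8, 4.9) | Principal Investigator | Yes, stated |
| Assesses outcome (4.8) | A medical assistant at the clinic | Stated to be blinded |
| Assesses efficacy at all visits (4.9) | Principal Investigator | Yes, as therapist |
| Makes all assessments (4.11) | Assessors, not further identified | Stated to be blinded |

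**2. Does withholding the block size protect the assessment?** No. It makes the next assignment harder to predict. It does not stop the allocating assistant from learning an assignment once made.

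**3. Is separation stated anywhere?** Not for the envelope handler. Section 4.5 does state it for another role: the physiotherapist in charge of rehabilitation takes no part in inclusion decisions or later evaluation. No equivalent bar applies to whoever allocates, and 4.9 runs against one for the therapist.

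**4. Do 4.9 and 4.11 agree?** No. If all assessments are made blind, the unblinded Principal Investigator cannot also assess efficacy at every visit. The 4.9 list names the clinical examination and the examination of the injured muscle as separate items, so efficacy assessment reads as something beyond routine clinical monitoring.

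**5. How many patients?** The total is 20 + 20 = 40.
- One assistant holds both roles and sees the assignments: 40 of 40 assessments are unblinded.
- The Principal Investigator's efficacy assessment supplies the outcome: 40 of 40.
- Two separate assistants, with 4.9 a drafting slip: 0 of 40.

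The text does not settle which of these applies.

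**The case against.** **The text implies separation.** An assistant who knows the arm could not meet the statement that the assessor is blinded, and 4.11 speaks of assessors in the plural. The list in 4.9 may be a general visit checklist that was not meant to define outcome assessment. This stands in part: nothing shows that one person will do both jobs, and the point is limited accordingly. But a promise of blinding does not say how it is kept, and 4.9 contradicts it in plain terms.

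**The concealment sentence.** A reader might infer more from it: that patients and staff learn the arm when recruitment closes. Recruitment is planned for about 12 months, and the secondary outcomes run to six months ("presence or absence of re-injury during a time period of six months after inclusion into the study"). With even accrual, 40 × 6/12 = 20 patients would then be told before their six-month outcomes are recorded. A reader might also infer that, patient by patient, concealment ends at enrolment and so all 40 are unblinded.

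The documents do not support either inference. The sentence concerns concealment of the assignment, and the word irrevocable fits each patient's own enrolment. Blinding of patients and of the assessor is stated in separate bullets with no end date. The sham handpiece in 4.5 looks and sounds like the active one, which serves to maintain patient blinding after allocation. Section 10.4 treats breaking the blind as a specific event, for pregnancy. No section provides for telling patients their arm when recruitment ends. The trial-wide reading would also hide the arm from the therapist who must deliver it from D5, so it is unlikely to be intended. What remains is loose wording: the sentence does not say whether it applies per patient or to the whole trial, and no section says when patient and assessor blinding ends.

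**Conclusion.** The point holds as a failure that the text permits, not one that it establishes. Section 4.8 describes allocator and blinded assessor identically without separating them, and 4.9 assigns randomization and efficacy assessment to the unblinded therapist, contrary to 4.2, 4.8 and 4.11. Depending on how the clinic staffs these roles, between none and all 40 return-to-play assessments could be made by someone who knows the arm. That range needs no assumption about accrual. The direction and size of any resulting bias cannot be computed from the document.

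The concealment sentence adds no unblinded patients to this count and is a matter of wording only.

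**What to change.** 1. **In 4.8**, state that anyone who prepares, holds or opens envelopes, or who delivers active or sham treatment, takes no part in assessing return to play (including clearance), re-injury or satisfaction.
2. **If the clinic has only one assistant**, that assistant assesses and never sees the envelope contents. The therapist opens the envelope, and only after the patient is recorded as irrevocably enrolled. That condition matters because, under 4.9, the same person checks eligibility.
3. **In 4.9**, amend the Principal Investigator's lists so that randomization and efficacy assessment match 4.8 and 4.11.
4. **As a clarification only**, say that allocation concealment runs until each patient is irrevocably enrolled, and that patient and assessor blinding runs until the last six-month outcome is recorded.

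The cost is a few sentences in 4.8 and a correction to 4.9. No extra staff are needed, and sample size, treatment and visit schedule do not change. The blinded assessor must be available whenever return to play is judged, which 4.11 already requires. Patients could learn their arm only after the last six-month outcome is recorded.

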4.9. Study treatment and visits

As outlined in Section 4.5 “Groups and treatments” above all subjects will perform RP that will last for eight weeks, independent of the individual time interval to return to play.

- The RP will start with a first visit to the clinic of the Principal Investigator during which clinical and ultrasonographic diagnosis will be performed. This first visit may take place on the day of injury (D0) or the first day (D1) or second day (D2) after injury (the sooner the better).
- After the first visit an individual number of days will follow until the fifth day after injury (D5) will be reached (acute phase). During this time the subject will apply the RICE principle (rest, ice, compression and elevation). Visits to the clinic of the Principal Investigator may be scheduled during this time but are not mandatory.
- On D5 the subacute/regeneration phase of the RP will start, with three visits per week to the clinic of the Principal Investigator (outlined in detail in Section 4.5 “Groups and treatments” above). The exact time for progression from the subacute/regeneration phase to the functional phase of the RP will be individually determined, depending on whether the criteria for progression will be fulfilled. During the functional phase there will also be three visits per week to the clinic of the Principal Investigator.
- Study treatments (rESWT or sham-rESWT) will start on D5. Each subject will be treated with nine sessions of rESWT or sham-rESWT, with three sessions per week. Accordingly, study treatments may take place at D5, D7, D9, D12, D14, D16, D19, D21 and D23.
- Six months after inclusion into the study there will be a separate visit for evaluating patient's satisfaction with the treatment outcome.

The time interval necessary for reaching return to play will be as follows:

- Based on our experience we expect that approximately 75% of the subjects treated with rESWT + RP will reach return to play within five weeks after D0.
- Furthermore, we expect that only approximately 25% of the patients treated with sham-rESWT + RP will reach return to play within five weeks after D0.

The Principal Investigator will perform the following procedures at the first visit:

- check eligibility
- obtain informed consent
- perform randomization
- collect patient's demographics & medical history

Furthermore, the Principal Investigator will perform the following procedures at all visits:

- record any concomitant medication
- perform clinical examination
- perform physical examination of the injured muscle
- dispense study treatment
- perform efficacy assessment
- report adverse events (AE) and serious adverse events (SAE)
- complete relevant section of case report form (CRF)

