It is of note that another study that was published very recently in the *The New England Journal of Medicine* demonstrated the negative clinical consequences of protracted immobilization after an acute muscle injury Type 3b in recreational sports. Starting rehabilitation two days after injury rather than waiting for nine days shortened the interval from injury to pain-free recovery and the time to return to play by approximately three weeks without any significant increase in the risk of reinjury (Bayer et al., 2017). The authors of this study concluded that the observed difference supports the importance of early loading of injured musculotendinous tissue.

According to Müller-Wohlfahrt et al. (2013) acute muscle injuries Type 3a and 3b have different time frames for recovery and return to play, with optimal treatment between 10 and 14 days in case of Type 3a and on average approximately six weeks in case of Type 3b (see also Figs 5 and 6). However, particularly in case of acute HMC injury Type 3b there is considerable interindividual variability in the time frame for return to play (Figs 5 and 6).

Most importantly, particularly the high reinjury rate of acute HMC injury suggests

that commonly utilized rehabilitation programs may be inadequate at resolving possible muscular weakness, reduced tissue extensibility, and/or altered movement patterns associated with the injury (Heiderscheit et al., 2010). Accordingly, there is need for developing innovative treatment options particularly for acute HMC injury Type 3b.

Figure removed because of copyright reasons

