3.2. Specific Objectives

- 1) To determine the individual and mean time to return to play after treating acute HMC injury Type 3b with respectively rESWT + RP or sham-rESWT + RP.
- 2) To determine the incidence of re-injury during a period of six months after return to play following treatment of acute HMC injury Type 3b with respectively rESWT + RP or sham-rESWT + RP.
- 3) To evaluate patient's pain score during respectively rESWT or sham-rESWT for acute HMC injury Type 3b using the Visual Analogue Scale (VAS) score.
- 4) To evaluate patient's satisfaction at six months after the end of treatment.

4. Study protocol

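### Re-injury must be confirmed by clinical and ultrasound findings, yet for about 124 days of its six-month window no visit is scheduled and no trigger is expressly tied to that outcome

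*Protocol*

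**What the plan says.** **The outcome.** Protocol Section 4.10.2 lists "presence or absence of re-injury during a time period of six months after inclusion into the study" as a secondary outcome. The event is abrupt pain at the back of the thigh first injured, "accompanied by the same objective criteria initially used for the diagnosis of acute HMC injury Type 3b". Section 4.3 shows what those criteria are: "Adults (both male and female) with clinical and ultrasonographic diagnosis of acute HMC injury Type 3b". Section 5 compares the yes/no result between arms with Fisher's exact test.

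**The contacts.** Section 4.9 states that "all subjects will perform RP that will last for eight weeks, independent of the individual time interval to return to play". The programme begins at the first visit (D0 to D2), and from D5 there are three clinic visits a week. After that, Section 4.9 names one more contact: "Six months after inclusion into the study there will be a separate visit for evaluating" satisfaction with the result. Section 5 points to Section 4.10 for follow-up, and that section adds no visit, call or diary. The list of procedures for all visits in Section 4.9 includes examination of the injured muscle and adverse-event reporting. Ultrasound is named there only for the first visit.

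**The club pathway.** Under recruitment, Section 4.6 tells club officials that athletes with abrupt posterior-thigh pain must stop. It continues: "These athletes will then be evaluated regarding the presence of the inclusion criteria of this study on the day of injury".

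**The window.** Section 3.2 defines it differently from Section 4.10.2: "To determine the incidence of re-injury during a period of six months after return to play".

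**The concern.** The definition asks for findings that are present while the injury is recent, but the schedule stops looking after about eight weeks. A player who tears the muscle again in month 3 or 4 and reports it at the six-month visit can describe the pain. That visit may no longer be able to show the clinical and ultrasound findings.

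Re-injury is specific objective 2, and the background section gives the high re-injury rate as a reason for seeking new treatments. It is also the natural check on whether faster return to play has a price, since Section 4.9 expects 75% of the active arm and 25% of the sham arm back within five weeks.

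The numbers are small. The background cites 8 recurrences among 32 previously injured players over 12 months (25%). Even if that whole 25% fell within six months, it would give 0.25 × 20 = 5 events per arm. One or two missed events would matter. An analysis plan cannot repair this, because an ultrasound not taken at the time cannot be recovered.

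**Working it through.** The plan gives no figure for how completely re-injury will be ascertained. Its power figures in Section 5.1 concern return to play and do not enter here.

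**Inputs**
- Programme length: 8 weeks = 56 days from a first visit at D0 to D2 (Section 4.9).
- Six-month visit: taken as D182.
- Recovery time after a Type 3b injury, all from the background section: "on average approximately six weeks in case of Type 3b", i.e. 42 days (Treatment); medians of 62.5 and 83 days (Figure 6 caption); range 14 to 105 days (Figure 5 caption).

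**Step 1: length of the gap**
- Latest programme end: 2 + 56 = D58.
- Gap: 182 − 58 = 124 days; 124 / 182 = 68% of the window.
- With the programme ending at D56, the gap is 126 days (69%).

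**Step 2: share of gap re-injuries already recovered at the six-month visit**

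Assumptions: re-injuries fall evenly over the gap, none is reported earlier, and return to play is a rough proxy for loss of clinical and ultrasound signs. With recovery time h, the share is (124 − h) / 124.

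| h (days) | Calculation | Share |
|---|---|---|
| 14 | 110 / 124 | 89% |
| 42 | 82 / 124 | 66% |
| 62.5 | 61.5 / 124 | 50% |
| 83 | 41 / 124 | 33% |
| 105 | 19 / 124 | 15% |

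A 126-day gap moves these shares by less than two percentage points.

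**Step 3: how far the club pathway could help**

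Suppose the pathway also caught enrolled players, ended with recruitment at 12 months, and enrolment was even over 365 days. A point t days after inclusion is then covered with probability 1 − t/365. The mean t over the gap is (58 + 182) / 2 = 120, so coverage is 1 − 120/365 = 67% of gap person-time. Part of the gap would stay open even on this favourable reading, chiefly for late enrollees.

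**Step 4: the two windows**

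Section 4.10.2 and Section 5 count six months from inclusion. Section 3.2 counts from return to play. Under Section 3.2, a player back at day R has a window ending near R + 182, so about R days follow the last visit: 35 days for a return at D35, 42 for a return at D42.

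**The case against.** **The club pathway is a real trigger.** All patients come from one club. The instruction does not exclude enrolled players, its pain trigger is close to the re-injury definition, and an inclusion check would involve the clinical and ultrasound diagnosis that definition needs. This stands in part: a reader might infer that nothing at all would prompt an examination, and the document does not support that. But the instruction sits under recruitment and tests eligibility. Section 4.4 excludes anyone with a hamstring injury of the same limb in the previous six months, so a re-injured participant would simply screen out. Nothing sends the result to the outcome record, and the instruction may lapse after about 12 months.

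**The six-month visit is more than a satisfaction question.** This also stands in part. The list for all visits brings muscle examination and adverse-event reporting, and Section 10.2 records events that patients volunteer. A past event may therefore be heard of. Ultrasound is not on that list, and an examination at six months cannot supply findings from months earlier.

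**Unconfirmed events need not be lost.** A reader might infer that recalled events are coded as no re-injury. No section says so, and an examination made elsewhere at the time could satisfy the definition. The plan is silent on both.

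**Early returners are watched.** A player back by D35 has at least 56 − 35 = 21 days of play with three clinic visits a week. This is correct, and it limits the concern to the period after the programme.

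**Conclusion.** The point holds as a gap in ascertainment. For about 124 of 182 days the protocol schedules no contact and has no trigger expressly tied to an outcome that depends on objective findings. Some re-injuries could not be confirmed, and the outcome may be under-ascertained.

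The size is uncertain. The share recovered before the six-month visit runs from 66% at the six-week average to 33% at the longer median, and from 89% to 15% over the cited range. All of these assume even timing and no earlier reporting. They also use return to play in place of disappearance of signs, which the protocol does not equate.

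A reader might infer that most re-injuries in the gap would have healed unseen. That follows only from the shorter recovery figures, and spontaneous reporting or the club pathway would lower every share. Nor does the document show that the arms would be made to look alike. What can be said is that missed events weaken a comparison with 20 patients per arm. This is a cheap improvement worth making.

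**What to change.** 1. In Sections 4.6 and 4.9, extend the instruction to club officials to enrolled patients until the re-injury window closes, whether or not recruitment has ended. Sudden posterior-thigh pain in the leg first injured should lead to the same clinical and ultrasound evaluation as at entry, by an assessor blind to allocation (as Section 4.11 already requires of follow-up assessments), recorded as re-injury yes or no.
2. In Section 4.9, name re-injury in the purpose of the six-month visit. Adverse-event reporting is already on the list for all visits.
3. Reconcile the window: Section 3.2 starts it at return to play, Sections 4.10.2 and 5 at inclusion. If the Section 3.2 start is kept, the instruction and the last contact must run to its later end.

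**Cost:** a few sentences and a further notice to one club that is already instructed. The downside is one unscheduled examination with ultrasound per suspected re-injury, which the outcome definition already presupposes.
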